7.2.2. Imaging Assessments for RECIST v1.1 and mRECIST v1.1

Details of response assessments are described in [Appendix 4](#), [Appendix 5](#) and [Appendix 6](#).

Brain lesions will be assessed by mRECIST v1.1 criteria. Modification of RECIST v1.1 allows up to 5 intracranial target lesions of 5 to 40 mm in diameter and includes target lesions measuring 5 to 10 mm in their longest diameter. Brain lesions will be measured only by gadolinium-enhanced MRI, with a scan-slice thickness of 1 mm for metastases with a longest diameter of 5 to 10 mm.

7.2.3. Blinded Independent Central Review

All radiological assessments obtained for patients will be centrally collected by an imaging vendor designated by the Sponsor and may be assessed centrally by a BICR in addition to the local (Investigator) assessment if deemed necessary.

7.2.4. Post-treatment Follow up

All AEs suspected to be related to study treatment should be followed up weekly, or as clinically indicated, until resolution or stabilization. In addition, dermatologic screening for skin malignancies should be performed every 2 months until 6 months after the last dose of encorafenib.

7.2.4.1. 30-Day Safety Follow Up

All patients will return for a 30-Day Safety Follow-up Visit 30 ± 7 days after the last dose of study drug, or prior to starting subsequent anticancer therapy, whichever occurs first. Information related to AEs (including concomitant medication taken for ongoing AEs) and ongoing antineoplastic treatments will be collected for 30 days after the last dose of study drug.

7.2.4.2. Disease Follow Up

Patients who discontinue study treatment for a reason other than disease progression will move into the disease status follow up and should be assessed every 8 weeks (± 7 days) by

radiological imaging to monitor disease status. Every effort should be made to collect information regarding disease status until:

- The start of new anticancer therapy.
- Disease progression.
- Death.
- The end of study.

7.2.4.3. Survival Follow up

Once a patient has received the last dose of study treatment, has confirmed disease progression or starts a new anticancer therapy, the patient moves into the Survival Follow-up Period and should be contacted by telephone, email or site visit to undergo the following assessments at least every 12 weeks (\pm 7 days) until withdrawal of consent, the patient is lost to follow up, death or defined end of the study, whichever occurs first:

- Record new SAEs that are considered related to study drug.
- Record all subsequent anticancer therapies.
- Determine survival status.

7.2.5. Performance Status

Assessments of ECOG PS and Karnofsky Status will be conducted as shown in Table 9 (Oken et al, 1982) at the time points specified in the SoA (Table 3).

Table 9. Performance Status Scoring

Karnofsky Status	Karnofsky Grade	ECOG Grade	ECOG Performance Status
Normal, no complaints	100	0	Fully active, able to carry on all pre-disease performance without restriction
Able to carry on normal activities. Minor signs or symptoms of disease	90	1	Restricted in physically strenuous activity but ambulatory and able to carry out work of a light or sedentary nature, e.g., light house work, office work
Normal activity with effort	80	1	Restricted in physically strenuous activity but ambulatory and able to carry out work of a light or sedentary nature, e.g., light house work, office work
Care for self. Unable to carry on normal activity or to do active work	70	2	Ambulatory and capable of all self-care but unable to carry out any work activities; up and about more than 50% of waking hours
Requires occasional assistance, but able to care for most of his needs.	60	2	Ambulatory and capable of all self-care but unable to carry out any work activities; up and about more than 50% of waking hours

Table 9. Performance Status Scoring

Karnofsky Status	Karnofsky Grade	ECOG Grade	ECOG Performance Status
Requires considerable assistance and frequent medical care	50	3	Capable of only limited self-care; confined to bed or chair more than 50% of waking hours
Disabled. Requires special care and assistance	40	3	Capable of only limited self-care; confined to bed or chair more than 50% of waking hours
Severely disabled. Hospitalization indicated though death non-imminent	30	4	Completely disabled; cannot carry on any self-care; totally confined to bed or chair
Very sick. Hospitalization necessary. Active supportive treatment necessary	20	4	Completely disabled; cannot carry on any self-care; totally confined to bed or chair
Moribund	10	4	Completely disabled; cannot carry on any self-care; totally confined to bed or chair
Dead	0	5	Dead

7.2.6. BRAF Testing

Patients will be eligible for the study based on identification of a *BRAFV600* mutation in tumor tissue as determined by a local laboratory PCR or NGS-based assay. Patients must have written documentation from a previous local laboratory pathology report of a *BRAFV600* mutation.

The investigator must confirm prior to enrollment that the patient has adequate tumor tissue available to determine *BRAFV600* mutation status by a central laboratory. All patients are required to submit either an archived tumor tissue sample or a newly obtained core or excisional biopsy (fine needle aspiration is not adequate for either archival or new tissue samples).

For archival tumor tissue samples, whenever possible the sample sent for central testing should be from the same tumor block that was used for local testing. A minimum of 8-15 unstained slides or 1 block of tissue should be submitted to the central laboratory. Further details regarding sample submission including instructions for sample processing and shipping will be provided in the Laboratory Manual. If a biopsy is taken, the biopsy should be taken from a non-target lesion. If the patient is enrolled based on local assay results, the *BRAF* mutation status must be evaluated by a central laboratory no later than 30 days from first dose of study treatment.

In cases where there is discordance between the local assay and central laboratory results, or if a central laboratory is not able to confirm presence of a *BRAFV600* due to inadequate or poor sample condition within 30 days of initiating study therapy, patients may only continue treatment if there is no clinical indication of deterioration or disease progression and the Investigator determines that the patient is deriving clinical benefit. In such instances, patients

must be informed that the *BRAF* mutation status is unconfirmed and must sign a separate ICF. Patients with discordant local and central results will be replaced.

Central laboratory *BRAF* mutation tests with a definitive result (positive or negative) may not be repeated to resolve a discordant result unless a biopsy sample from a different tumor lesion can be provided. Patients whose sample is determined inadequate or who have an indeterminate result on central testing may have samples resubmitted for testing.

7.3. Safety Assessments

The Sponsor Medical Monitor, or designee, and the Sponsor's Drug Safety and Pharmacovigilance Department will be responsible for the ongoing review and evaluation of safety data, including AEs, laboratory data and any other safety evaluations, throughout the duration of the study.

Planned time points for all safety assessments are provided in the SoA ([Table 3](#)).

7.3.1. Patient Demographics and Other Baseline Characteristics

Demographic data, medical, surgical and social history will be collected at Screening.

7.3.2. Disease Characteristics and Treatment History

A history of present illness (disease-specific medical history) will be collected at Screening. Details regarding the patient's malignancy under study, including date of diagnosis, cancer stage at diagnosis, tumor histology and prior treatments will be recorded.

7.3.3. Physical Examinations

Physical examinations will be performed by trained medical personnel at the time points specified in the SoA ([Table 3](#)).

At Screening, the physical examination will include the examination of general appearance, skin, neck (including thyroid), eyes, ears, nose, throat, lungs, heart, abdomen, back, lymph nodes, extremities, vascular and neurological. If indicated based on medical history or symptoms, rectal, external genitalia, breast and pelvic examinations will be performed.

Body weight will be measured as part of the physical examination at each visit. Height will be measured only at Screening. For subsequent visits, the physical examinations will be targeted as clinically indicated.

Investigators should pay special attention to clinical signs related to previous serious illnesses.

All physical examinations occurring on dosing days must be performed prior to study drug administration. Any treatment-emergent abnormal findings will be recorded as AEs.

7.3.4. Dermatological Examinations

Dermatologic evaluations will be performed at the site by the Investigator to monitor for the possible development of keratoacanthoma and/or squamous cell carcinoma, as these have

been reported to occur with selective BRAF inhibitor treatment (Flaherty et al, 2010, Kefford et al, 2010, Robert et al, 2011). This assessment may be performed predose or postdose at the time points specified in Table 3. In addition, dermatologic screening for skin malignancies will be performed every 8 weeks until 6 months after the last dose of encorafenib.

In case of occurrence of keratoacanthoma or squamous cell carcinoma, patients will undergo complete surgical excision of the skin lesion following institutional standards. Dermatologic evaluations should be performed by a dermatologist as clinically indicated.

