- **New primary malignancies:** Based on its mechanism of action, encorafenib may promote malignancies associated with activation of *RAS* through mutation or other mechanisms. Cutaneous and non-cutaneous malignancies occurred in patients,

- including cutaneous squamous carcinoma/keratoacanthoma (2.6%) and basal cell carcinoma (1.6%).
- **Left ventricular dysfunction:** Symptomatic or asymptomatic decreases in ejection fraction occurred in 7% of patients, with Grade 3 left ventricular dysfunction occurring in 1.6% of patients.
 - **Hemorrhage:** Hemorrhage occurred in 19% of patients, with events \geq Grade 3 occurring in 3.2% of patients. Fatal intracranial hemorrhage in the setting of new or progressive brain metastases occurred in 1.6% of patients. The most frequent hemorrhagic events were gastrointestinal, including rectal hemorrhage (4.2%), hematochezia (3.1%), and hemorrhoidal hemorrhage (1%).
 - **Venous thromboembolism:** Occurred in 6% of patients, including 3.1% of patients who developed pulmonary embolism.
 - **Ocular toxicities:** Serous retinopathy is a class effect of MEK inhibitors. It is generally asymptomatic or mildly symptomatic and reversible ([Uerner-Bloch et al, 2016](#)). Serous retinopathy occurred in 20% of patients. Symptomatic serous retinopathy occurred in 8% of patients with no cases of blindness. The median time to onset of the first event of serous retinopathy (all grades) was 1.2 months. RVO is a known class-related adverse reaction of MEK inhibitors and may occur in patients treated with binimetinib in combination with encorafenib. In patients with *BRAF* mutation-positive melanoma across multiple clinical trials, 0.1% of patients experienced RVO. Uveitis, including iritis and iridocyclitis, has been reported in patients treated with encorafenib in combination with binimetinib. In the COLUMBUS study, the incidence of uveitis among patients treated with encorafenib 450 mg QD in combination with binimetinib 45 mg BID was 4.4%.
 - **Pneumonitis/Interstitial Lung Disease:** Pneumonitis occurred in 0.3% of patients with *BRAF* mutation-positive melanoma across multiple clinical trials.
 - **Hepatotoxicity:** The incidence of Grade 3 or 4 increases in liver function laboratory tests was 6% for alanine aminotransferase (ALT), 2.6% for aspartate aminotransferase (AST), and 0.5% for alkaline phosphatase. No patient experienced Grade 3 or 4 serum bilirubin elevation.

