7.4.1. Time Period and Frequency for Collecting AE and SAE Information

The time period for actively eliciting and collecting AEs and SAEs ("active collection period") for each patient begins from the time the patient provides informed consent, which is obtained before the patient's participation in the study (ie, before undergoing any study-related procedure and/or receiving study treatment), through and including a minimum of 30 calendar days, except as indicated below, after the last administration of the study treatment.

During the long-term follow-up period in this study for survival, only SAEs will be actively elicited and collected after completion of the active collection period described above. The SAEs identified during long-term follow-up will be reported to Pfizer Safety on the CT SAE Report Form only if considered reasonably related to the study treatment.

Follow-up by the investigator continues throughout and after the active collection period and until the AE or SAE or its sequelae resolve or stabilize at a level acceptable to the investigator and Pfizer concurs with that assessment.

For patients who are screen failures, the active collection period ends when screen failure status is determined.

If the patient withdraws from the study and also withdraws consent for the collection of future information, the active collection period ends when consent is withdrawn.

If a patient definitively discontinues or temporarily discontinues study treatment because of an AE or SAE, the AE or SAE must be recorded on the CRF and the SAE reported using the CT SAE Report Form.

Investigators are not obligated to actively seek AEs or SAEs after the patient has concluded study participation. However, if the investigator learns of any SAE, including a death, at any time after a patient has completed the study, and he/she considers the event to be reasonably related to the study treatment, the investigator must promptly report the SAE to Pfizer using the CT SAE Report Form.

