3.4. Safety Endpoints

Safety endpoints will be summarized based on the on-treatment period unless otherwise specified. Safety data collected outside the on-treatment period will be listed but not summarized.

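### Skin-cancer screening runs to 6 months after the last encorafenib dose, but after the 30-day period only SAEs are collected and no AE table counts what is found

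*Protocol*

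**What the plan says.** **Surveillance.** Protocol 7.3.4 names keratoacanthoma and squamous cell carcinoma as the lesions to watch for and states that "dermatologic screening for skin malignancies will be performed every 8 weeks until 6 months after the last dose of encorafenib". Protocol 7.2.4 repeats the requirement with a slightly different interval: "dermatologic screening for skin malignancies should be performed every 2 months until 6 months after the last dose of encorafenib". New primary malignancy comes first among the important potential adverse effects in 2.2.3, the section to which 7.4.8 refers for AESIs. In Table 3 the dermatologic examination appears at the end-of-treatment and 30-day visits, with no entry under survival follow-up.

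**Collection.** Protocol 7.4.1 runs active AE and SAE collection "through and including a minimum of 30 calendar days, except as indicated below, after the last administration of the study treatment". In survival follow-up, "only SAEs will be actively elicited and collected after completion of the active collection period described above", and these go to the sponsor's safety group "only if considered reasonably related to the study treatment". The instruction in 7.2.4.3 for survival contacts is narrower: "Record new SAEs that are considered related to study drug". Those contacts are at least every 12 weeks and may be by telephone or email. Under 7.4.1.2, recording of non-serious AEs ends sooner if new anticancer therapy starts.

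**Analysis.** SAP 3.4.1 and 5.2.5 close the TEAE window and the on-treatment period at last dose + 30 days, or earlier with subsequent therapy. SAP 3.4 adds: "Safety data collected outside the on-treatment period will be listed but not summarized". SAP 6.6.1 bases its AE analyses on TEAEs unless otherwise specified and defines no summary of new primary malignancies. The SAP version history records that the dermatology listing was removed.

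**The concern.** The protocol asks patients and sites for about five further months of skin examinations because of a named drug risk, yet sets no matching rule for recording or tabulating the findings. Further evaluation of the safety profile is a stated secondary objective. If the plan is followed as written, some findings from a mandated examination need not enter the AE data at all. Those that do enter are kept out of every AE incidence table. A reader of the study report could take the tabulated malignancy count as the yield of the whole surveillance programme, when it covers only the part up to 30 days after treatment.

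**Working it through.** The plan states no figure on this point that could be reproduced. The check is one of aligning windows.

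**Inputs**
- Screening window: 6 months after last encorafenib (Protocol 7.2.4, 7.3.4).
- Month length: 30.4375 days (SAP 5.2.11).
- AE table limit: last dose + 30 days (SAP 3.4.1, 5.2.5).
- 30-day visit tolerance: ± 7 days (Protocol 7.2.4.1).

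**Do the two clocks start together?** Yes. Under Protocol 6.7.1 a patient who permanently stops encorafenib must also stop binimetinib. The last encorafenib dose is therefore in effect the last dose of study treatment.

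**Share of the window beyond day 30**
- Window = 6 × 30.4375 = 182.6 days.
- Beyond day 30 = 182.6 − 30 = 152.6 days.
- Share = 152.6 / 182.6 = 83.6%.
- If the cut were at day 23 or day 37 (the visit tolerance), the share would be 87.4% or 79.7%.

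**Where the examinations fall** (assuming the interval restarts at last dose)
- Every 8 weeks: days 56, 112, 168.
- Every 2 months: days 61, 122, 183.

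All six dates are after day 30. On that spacing, the only post-treatment skin examinations that can yield a TEAE are those at the end-of-treatment and 30-day visits.

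**What happens to a lesion first found after day 30**

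| Investigator's rating | Collected? | In an AE table? |
|---|---|---|
| Non-serious | No stated route (7.4.1) | No |
| Serious, unrelated | Elicited under 7.4.1; not recorded under 7.2.4.3 | No |
| Serious, related | Yes (7.4.1, 7.2.4.3) | No; listing only (SAP 3.4, 6.6.1) |

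**How many cases?** This cannot be derived. The 2.6% (cutaneous squamous carcinoma/keratoacanthoma) and 1.6% (basal cell carcinoma) in Protocol 2.2.3 are overall rates on the combination, with no split by time since last dose. As an assumption, take a risk after day 30 of 0.5% to 2.6%. The upper end borrows the first of those rates as a ceiling for illustration. Phase 2 closes when either cohort reaches about 50, so take 50 to 100 patients:
- Lowest: 0.005 × 50 = 0.25 cases.
- Highest: 0.026 × 100 = 2.6 cases.
- Chance of at least one case in 100 patients, 1 − (1 − p)^100: 0.39 at 0.5% and 0.93 at 2.6%.

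**The case against.** The strongest reply is that these events are not lost. SAE collection continues through survival follow-up, and Appendix 7 gives invasive or malignant cancers as an example of events that should usually be treated as serious. A squamous cell carcinoma fits that wording, and a basal cell carcinoma arguably does. Causality that the investigator does not know is handled as related for reporting. Captured late events are listed under SAP 3.4 and 6.6.1, and SAP 6.6.2 tabulates all deaths whenever they occur. With so few cases, a listing shows every one. This stands, and it defeats one tempting inference, that AE collection simply stops at 30 days and that malignancies found later are missed. The gap in collection is confined to lesions rated non-serious, such as some keratoacanthomas, and serious ones judged unrelated.

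Second, a TEAE rate to last dose + 30 days is correct for its stated window, and no endpoint is defined as malignancy incidence to 6 months. This also stands: no planned number is wrong. What is missing is a number that matches the surveillance.

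Third, Protocol 7.3.4 presents the 8-weekly screening as additional to the Table 3 time points, so the absence of a later Table 3 entry is not a contradiction. That is fair. Still, survival contacts need not be visits, so the schedule shows no occasion at which the examination is done or recorded.

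Fourth, counting events after new anticancer drugs makes attribution hard in an uncontrolled study. This is a real cost, which flagging such events meets in part.

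**Conclusion.** The mismatch holds. About 84% of the post-treatment screening window lies outside the period the AE tables cover, and within it non-serious skin neoplasms have no stated route into the AE data. Serious neoplasms judged unrelated fall between 7.4.1 and 7.2.4.3, and captured serious ones reach listings only. The 84% is a share of the post-treatment window, not of total time at risk including treatment.

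A reader might add the two rates in Protocol 2.2.3, expect about four cases in 100 patients, and infer that missing one or two would shift the reported rate by a quarter to a half. The documents do not support that. They give no post-treatment rate and no basis for the number missed, and adding the rates assumes no patient has both lesions. The 0.25 to 2.6 cases above are an illustration resting on the assumed 0.5% to 2.6% risk.

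The primary endpoint and the existing TEAE analyses are untouched. The change is worth making because it is specific and cheap, and because the examinations are already required.

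**What to change.** **Protocol**
- 7.4.1: state that any new primary malignancy or skin neoplasm found at the already required screening is recorded as an AE through 6 months after the last encorafenib dose, whatever its seriousness or relatedness.
- 7.2.4.3 and 7.4.1: reconcile whether all SAEs or only related ones are recorded in survival follow-up.
- Table 3: show the post-treatment skin examinations that 7.2.4 and 7.3.4 require, and reconcile the 2-month and 8-week wording of those two sections.

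**SAP 6.6.1**
- Add one supplementary summary of new primary malignancies, counted from first dose to last encorafenib dose + 6 months, with events after the start of subsequent anticancer therapy flagged. Place it beside the TEAE tables, which stay unchanged.

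**Cost.** A short protocol wording change, one SAP table and slight extra recording, including for patients otherwise followed by telephone or email. No examination is added. Attribution will be harder for events after subsequent therapy, which is why those should be flagged and the summary kept supplementary.

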7.3.5. Vital Signs

Vital sign measurements (to be taken before blood collection for laboratory tests) will be measured per institutional standards as part of the physical examination at the time points specified in SoA (Table 3). Vital sign assessments include the following:

- Temperature, pulse rate, respiratory rate and blood pressure will be assessed.
- Blood pressure and pulse measurements will be assessed with a completely automated device. Manual techniques will be used only if an automated device is not available. Blood pressure and pulse measurements will be preceded by at least 5 minutes of rest for the patient in a quiet setting without distractions (e.g., television, cell phones).

All vital sign measurements occurring on dosing days must be performed prior to study drug administration. Abnormal vital sign results identified after the first dose of study treatment constitute an AE if they are considered clinically meaningful, induce clinical signs or symptoms, require concomitant therapy or require changes in study treatment.

